SOC	Standard of Care
SOP	Standard Operating Procedure
UP	Unanticipated Problem
US	United States
UVA	University of Virginia
VPR	Vice President for Research

1 PROTOCOL SUMMARY

1.1 Synopsis

Title: A Randomized Controlled Trial of Topical Cannabidiol for the Treatment of Thumb Basal Joint Arthritis.

Study Description: To investigate the therapeutic potential of cannabidiol (CBD) as a topical treatment for thumb basal joint arthritis. **Rationale:** CBD is commonly being used as an over-the-counter treatment for arthritis-related pain, however no clinical trial has been performed to establish efficacy. **Hypothesis:** CBD is more effective than placebo for relieving pain and improving patient-reported outcomes for thumb basal joint arthritis.

Study Design: The study design will be a double-blind, randomized controlled trial with crossover. Treatment will be blinded to the subjects and investigators. Patients will be randomly assigned 2 weeks of the CBD or control and then crossover to the other condition for 2 additional weeks. Patients will apply a novel cream containing CBD at the thumb base joint twice daily for 1 hour. Subjects will be advised to observe for physiologic changes, skin changes, or other adverse effects.

Objectives & Endpoints:	Objectives	Endpoints
	Primary	
	To determine the therapeutic potential of CBD as a topical treatment for thumb basal joint arthritis.	
Hand Functional Assessment: Change from baseline hand functional assessment including grip, appositional, and oppositional pinch strength (kg); Kapandji score; and metacarpal phalangeal (MP) and interphalangeal (IP) range of motion.
 
Patient Reported Outcome Measures: Change from baseline in the PROMIS-29 (Patient-Reported Outcomes Measurement Information System) and PROMIS upper extremity tests. The PROMIS-29 is a free publicly available generic health related quality of life (HRQoL) measure consisting of indices of pain, pain interference, depression, anxiety, global function, and social interactions. The PROMIS upper extremity test utilizes item-response theory and Computer Adaptive Test to efficiently and precisely report patient symptoms and perceived function.

	Secondary	


To determine the safety of treatment CBD.
	
Safety will be determined by evaluating:
 
 • The frequency and severity of adverse events from the beginning of treatment through the end of study participation. • Changes in skin appearance from baseline using standardized skin assessment tool. (patient will be removed from study with a score ≥ 2) • Clinically significant change in CBC (baseline and follow-up) • Clinically significant change in basic metabolic panel (i.e., BUN, creatinine, CO₂, Cl, K, Na, and glucose) (baseline and weekly follow-up) • Clinically significant change in hepatic function testing (i.e., serum transaminases [ALT/AST], total bilirubin, and alkaline phosphatase) (baseline and weekly follow-up) • Clinically significant change in vital sign assessments (i.e., heart rate and blood pressure) (baseline and weekly follow-up) • Suicidal behavior and thoughts as a specific question using the Columbia-Suicide Severity Rating Scale (C-SSRS) (baseline and weekly follow-up)
--	--

Study Population: 40 subjects with presenting with thumb basal joint arthritis over the age of 18 will be recruited from the UVA Hand Center.

Description of Sites/Facilities This will be a single-site study conducted at the UVA Hand Center at the University of Virginia.

Enrolling**Participants:****Description of****Study****Intervention:**

[figure not shown]
The study design will be a double-blind randomized control trial with crossover. Treatment will be blinded to the subjects and investigators. Patients will be randomly assigned two (2) weeks of the case (CBD) or control cream and then crossover to the other cream for two (2) additional weeks. Patients will apply the topical cream at their thumb basal joint twice daily for 1 hour. The subjects will be advised to observe for physiologic changes, skin changes, or other adverse effects. If mild to serious adverse events are noticed, the creams will be removed immediately and appropriate care and observation will be taken. Each condition will last for 2 weeks and then subjects will be contacted by the study coordinator to facilitate crossover into the other condition. To capture any delayed-onset adverse events, including those related to skin changes that might develop after the drug is discontinued, subjects will attend a follow-up visit seven (7) days following the last dose of investigational cream.

Study**Duration:****Participant****Duration:**

This study will last one year from the beginning of subject recruitment to data analysis.

Subjects will be enrolled in this study for approximately six (6) weeks from Screening until the final Study Visit.

1.2 Schema

2 INTRODUCTION

2.1 Study Rationale

Arthritis of the thumb basal joint is common, leading to debilitating pain, weakness, and instability that severely limits function (1). Cannabidiol (CBD) is a non-psychoactive hemp derivative with demonstrated efficacy for reducing cancer-related pain; however, its role in the treatment of arthritis-related pain has yet to be established.

2.2 Background

Numerous studies have shown the safety and efficacy of topical CBD for the treatment of osteoarthritis in dogs (2) and rats (3). Topical administration has been shown to have increased regional bioavailability and attenuates inflammation and pain without significant side-effects. The dose of maximum absorption and efficacy seen in rats was shown to be 6.2 mg/day (3). To date, no studies have been performed to evaluate the safety and efficacy of topical CBD for the treatment of basal thumb arthritis in human subjects.

Nitecka-Buchta et al. performed a double-blind randomized controlled trial of topical CBD for 60 total patients with myofascial pain. Topical application of 67 mg CBD – including other minor cannabinoids – was applied to masseter muscles twice daily for 14 days in the case group. Visual Analog Scores (VAS) were reduced from 5.6 on Day 0 to 1.7 on Day 14 (70.2% reduction) in the case group, versus 5.1 on Day 0 and 4.6 on Day 14 (9.8% reduction) in the control group ($p = 0.00$). (4)

Xu et al. performed a randomized controlled trial with cross-over for topical CBD treatment of 29 patients with symptomatic lower extremity neuropathy. Topical application of 250 mg of pure CBD (case arm) was applied up to four (4) times daily for four (4) weeks, and then patients switched to emu oil (control arm) with the same application for 4 weeks followed by cross-over. They showed a statistically significant reduction in Neuropathic Pain Scale scores for intense (5.11 to 4.02) ($p=0.009$) and sharp (4.01 to 3.09) ($p<0.001$) pain between case and control arms. (5)

No side effects or adverse events were noted in either clinical trial.

We have designed a randomized, controlled crossover design clinical trial to assess the safety and efficacy of topical CBD versus placebo for the treatment of thumb basal joint arthritis.

3 RISK/BENEFIT ASSESSMENT

3.1.1 Known Potential Risks

No major side effects were noted from previous topical studies. Minor side effects from topical and oral CBD studies include nausea, diarrhea, fatigue, change in appetite, and weight gain/loss (3). Exogenous CBD may affect the metabolism of Coumadin and other drugs based on the P450 metabolism. Another theoretical risk is contact dermatitis.

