4 OBJECTIVES AND ENDPOINTS

Objectives	Endpoints
Primary	
To determine therapeutic potential of CDB as a topical	Hand Functional Assessment: Change from baseline in hand functional assessment including grip, appositional,

treatment for thumb basal joint arthritis.	
and oppositional pinch strength (kg); Kapandji score; and MP and IP range of motion.
 
Patient Reported Outcome Measures: Change from baseline in the PROMIS-29 (Patient-Reported Outcomes Measurement Information System) and PROMIS upper extremity tests. The PROMIS-29 is a free publicly available generic health related quality of life (HRQoL) measure consisting of indices of pain, pain interference, depression, anxiety, global function, and social interactions. The PROMIS upper extremity test utilizes item-response theory and Computer Adaptive Test to efficiently and precisely report patient symptoms and perceived function.

Secondary	
To determine the safety of treatment CBD.
 
Safety will be determined by evaluating:
 
 • The frequency and severity of adverse events from the beginning of treatment through the end of study participation. • Changes in skin appearance from baseline using standardized skin assessment tool (patient will be removed from study with a score ≥ 2) • Clinically significant change in CBC (baseline and weekly follow-up) • Clinically significant change in basic metabolic panel (i.e., BUN, creatinine, CO₂, Cl, K, Na, and glucose) (baseline and weekly follow-up) • Clinically significant change in hepatic function testing (i.e., serum transaminases [ALT/AST], total bilirubin, and alkaline phosphatase) (baseline and weekly follow-up) • Clinically significant change in vital sign assessments (i.e., heart rate and blood pressure) • Suicidal behavior and thoughts as a specific question using the Columbia-Suicide Severity Rating Scale (C-SSRS) at baseline and follow-up.

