6 STUDY POPULATION

6.1 Inclusion Criteria

In order to be eligible to participate in this study, an individual must meet all of the following criteria:

1. Provision of signed and dated informed consent form.
2. Stated willingness to comply with all study procedures and availability for the duration of the study.
3. Male or female, aged 18 years or older.
4. Females of childbearing potential must have a negative urine and blood pregnancy test at Screening and a negative urine pregnancy test before study drug is administered. Females must abstain from sex or use a highly effective method of contraception during the period from Screening to administration of study drug and for 30 days after the last dose of study medication. Standard acceptable methods include abstinence or the use of a highly effective method of contraception, including; hormonal contraception, diaphragm, cervical cap, vaginal sponge, condom with spermicide, vasectomy, intrauterine device. If females are of non-child bearing potential, they must be post-menopausal defined as: age > 55 with no menses within the past 12 months, or history of hysterectomy, or history of bilateral oophorectomy, or bilateral tubal ligation.
5. Males must consent to use a medically acceptable method of contraception throughout the entire study period and for 90 days after their last study drug application. They must agree to not donate sperm for 90 days after their last study drug application.
6. Presence of radiographically confirmed diagnosis of thumb basal joint arthritis.

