9.2 Safety Assessments

Medical History: Relevant medical history, including history of mental illness, drug or substance abuse, history of hemp-based product usage and other pertinent history will be recorded in the case report form.

Laboratory Testing: At baseline and Study Day 35, blood draws will be performed on all subjects at the UVA Medical Laboratory. The following tests will be ordered and monitored for clinical abnormalities:

- CBC
- Basic metabolic panel (i.e., BUN, creatinine, CO₂, Cl, K, Na, and glucose)
- Hepatic function testing (i.e., serum transaminases [ALT/AST], total bilirubin, and alkaline phosphatase)
- Pregnancy Testing (if applicable) (Screening)
- Urine Pregnancy Test (if applicable) (Screening and Day 0 before dosing)

Daily Skin Monitoring: Subjects will be asked to observe the testing site for physiologic changes, skin changes or other adverse events daily. Subjects will be provided with a daily diary to record and monitor any observed changes. The daily diary is provided in Appendix 14.3. They will be instructed to notify the investigator of any sudden changes in skin appearance or increase in their arthritic symptoms that are more than minimally tolerated.

Physician Skin Monitoring: At baseline and at every subsequent visit, the investigator will assess the CBD cream site for adverse events. A score will be given corresponding to the assessment tool below:

Score	Definition
0	No erythema
1	Minimal erythema
2	Moderate erythema with sharply defined borders
3	Intense erythema with or without edema
4	Intense erythema with edema and blistering/erosion

- NOTE: Changes in skin appearance will be evaluated using the standardized skin assessment tool above. A patient will be removed from study with a score ≥ 2 .

Clinical Evaluations: Subjects will be monitored weekly for the following:

- Vital sign assessments (i.e., heart rate and blood pressure)
- Suicidal behavior and thoughts as a specific question using the Columbia-Suicide Severity Rating Scale (C-SSRS). The full questionnaire is provided in Attachment 3 (Appendix 14.4).
 - Monitor for somnolence and sedation and advise patients not to drive or operate machinery until they have gained sufficient experience on study drug. Subjects will be asked if they feel more, less, or no change in their level of fatigue during the time they were administering study drug.

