11 STATISTICAL CONSIDERATIONS

11.1 Statistical Hypotheses

Outcomes between the two groups will be compared and in a within-subject analysis will be performed given the crossover design. A descriptive analysis of the variables will be performed by calculating mean and standard deviation (SD), as appropriate, and absolute and percentage frequency. Differences between pre- and post-treatment scores (delta scores) will be assessed with the Wilcoxon signed-rank test. Correlations between delta scores and the variables considered [age, gender, body mass index (BMI), radiographic features] will be evaluated with the Spearman, Mann-Whitney, and Kruskal-Wallis tests. The significance threshold will be set at 0.05.

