14.3 Daily Sin Monitoring Diary

Day X	Time of onset	Time of symptom improvement	Time of symptom resolution
Itching			
Redness			
Red bumps/hives			
Swelling			
Diarrhea			
Nausea			
Change in appetite			
Fatigue			
Other concerning signs/symptoms			

Signature:

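### Weight change is a named CBD side effect and BMI a planned correlate, but no weight or height measurement is planned

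*Combined protocol and SAP*

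**What the plan says.** Section 3.1.1 (Known Potential Risks) lists five minor effects: "Minor side effects from topical and oral CBD studies include nausea, diarrhea, fatigue, change in appetite, and weight gain/loss". Section 3.1.2 then argues that safety monitoring mitigates the risks just described.

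The weekly clinical evaluations in 9.2 define vital signs narrowly: "Vital sign assessments (i.e., heart rate and blood pressure"). The safety endpoint in section 4 uses the same definition: "Clinically significant change in vital sign assessments (i.e., heart rate and blood pressure"). Medical history under 9.2 ends on an open item: "history of hemp-based product usage and other pertinent history will be recorded in the case report form".

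The diary in 14.3 has rows for diarrhea, nausea and fatigue, one for "Change in appetite", and a free-text row, "Other concerning signs/symptoms". It has no row for weight. The schedule in 14.1 has no row for weight, height or BMI at any of Visits 1 to 7.

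The analysis section (11.1) plans: "Correlations between delta scores and the variables considered [age, gender, body mass index (BMI), radiographic features"]. The only radiographic requirement is Inclusion 6: "Presence of radiographically confirmed diagnosis of thumb basal joint arthritis".

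**The concern.** Safety is the secondary objective, and the risk/benefit argument relies on the named risks being monitored. One of them, weight gain or loss, has no measurement and no prompt behind it. The other four effects each have a diary row, so the gap looks more like an oversight than a choice.

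Weight change is also the named effect that a scale settles most easily and that a subject who is not weighed is least likely to notice when it is small. A baseline weight that is not taken before the first cream cannot be recovered afterwards.

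On the analysis side, 11.1 commits to BMI as a correlate without saying where it comes from. Left open, BMI could be drawn from chart entries of varying date and completeness, or be missing for some subjects.

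**Working it through.** **Step 1: side effects against data capture.** This is a cross-check of sections, since the plan states no figure on this point to reproduce.

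| Effect named in 3.1.1 | Diary row (14.3) | Measured in 9.2 or 14.1 |
|---|---|---|
| Nausea | Yes | – |
| Diarrhea | Yes | – |
| Fatigue | Yes | Asked about in 9.2 |
| Appetite change | Yes | – |
| Weight gain or loss | No | No |

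Four of five have a dedicated prompt; one of five does not. Planned weight or height measurements across Visits 1 to 7: zero.

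**Step 2: is there a source for BMI?** In the text available, BMI appears only in 11.1, body weight only as the side effect in 3.1.1, and body height nowhere. The schedule's silence is not decisive on its own, because 14.1 also omits the weekly vital signs that 9.2 requires and has no row for age or gender. The point rests on 9.2 and 14.1 together: 9.2 limits vital signs to two items, neither of them weight, and no other procedure supplies weight or height.

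**Step 3: what weighing would give (illustration only).** The documents give no SD for weight change, so these inputs are assumptions:

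- SD of a two-week weight change: 0.7 to 1.5 kg.
- Correlation r between the two periods' changes: 0 to -0.5. A negative value is plausible because both changes share the Day 14 weight, so error in that reading moves them in opposite directions.
- All 40 subjects complete, with no carryover and no period effect.

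SD of the within-subject difference in change = SD × √(2(1 − r)), which is SD × √2 at r = 0 and SD × √3 at r = -0.5.

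95% half-width = 2.02 × SDdiff / √40:

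- SD 0.7: 2.02 × 0.990 / 6.325 = 0.32 kg (r = 0); 2.02 × 1.212 / 6.325 = 0.39 kg (r = -0.5).
- SD 1.5: 2.02 × 2.121 / 6.325 = 0.68 kg; 2.02 × 2.598 / 6.325 = 0.83 kg.

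Difference detectable with 80% power = 2.80 × SDdiff / √40:

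- SD 0.7: 0.44 kg (r = 0) to 0.54 kg (r = -0.5).
- SD 1.5: 0.94 kg to 1.15 kg.

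With n completers instead of 40, the half-widths grow by about √(40/n).

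**The case against.** A reader might infer that the trial will hold no information at all on weight and that the BMI analysis is impossible. The documents do not support that. Subjects see the diary's free-text row daily and staff review the diary at Visits 3 to 7. Adverse events are assessed at Visits 2 to 7 and are the first safety endpoint. Appetite change, a related symptom, is prompted. BMI could be recorded under the open medical-history item or taken from the medical record, and the case report form is not among the documents. These routes are real, but none is planned for this purpose and none involves putting a subject on a scale.

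A reader might also count radiographic features as a second correlate without data. That does not follow. Inclusion 6 requires radiographic confirmation, so films should exist and features can be read from them. At most the grading method is unstated, which is a separate and smaller matter.

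The importance can fairly be questioned. Section 3.1.1 pools topical and oral studies, and sections 2.2 and 5.2 report no side effects in either of the two human topical trials they cite. Weight is not a listed safety endpoint, and a protocol need not have an instrument for every potential risk. BMI does not touch the primary comparison, the sample size or any stopping rule. All of this stands, and it limits the point to a cheap improvement.

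The kilogram figures are also open to challenge. The SDs are assumed, and no weight change of clinical interest is given to judge them against. Treated subjects who withdraw are not replaced (8.2), stopping treatment means leaving the study (8.3), and the text describes no washout before the second cream is dispensed at Day 14. The figures are an illustration and the point does not depend on them.

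**Conclusion.** The point holds in a limited form. No weight or height measurement is planned in 9.2, 14.1 or 14.3, so weight change, one of five named side effects, can surface only through unprompted reports. BMI, one of four planned correlates, has no specified source.

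The consequence is modest: a minor effect, two-week periods, and a variable used only in correlations. The primary comparison is unaffected. The conclusion rests on the text supplied; the schema figure and the case report form were not available and could name a source. Any precision figure for weight change rests on the assumed SDs and correlations, on 40 completers and on no carryover.

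**What to change.** - Add body weight, on the same clinic scale, at Visits 2, 4 and 6 (Days 0, 14 and 28), and at Visit 7 (Day 35) for follow-up, to 9.2 and to the schedule in 14.1.
- Add height once at Visit 1.
- Report weight change by cream period (Day 0 to 14 and Day 14 to 28) as a descriptive safety measure, with the number of subjects contributing to each period.
- State in 11.1 that BMI is computed from the Visit 1 height and the Visit 2 weight, so that it precedes any study cream.
- If a precision statement is included, label it as resting on an assumed SD, 40 completers and no carryover.

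The cost is about a minute per visit, a few schedule cells and a few extra data fields. No visit is added, and the only equipment is a clinic scale.

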3.1.2 Assessment of Potential Risks and Benefits

A potential benefit of this treatment is the potential pain relief and gain of hand function if the CBD is effective at improving symptoms.

In addition – if the study shows that the administration of CBD cream will alleviate arthritic symptoms, this would be a cheap and easy treatment that could be used for many patients by delaying or potentially avoiding surgical intervention and improving their quality of life.

There has yet to be a randomized controlled trial demonstrating benefit of topical CBD products in this patients with osteoarthritis. The risks involved as detailed above are mitigated by safety monitoring and are outweighed by the ability to add to the current research in Cannabidiol products, which are currently understudied.

4 OBJECTIVES AND ENDPOINTS

Objectives	Endpoints
Primary	
To determine therapeutic potential of CDB as a topical	Hand Functional Assessment: Change from baseline in hand functional assessment including grip, appositional,

treatment for thumb basal joint arthritis.	
and oppositional pinch strength (kg); Kapandji score; and MP and IP range of motion.
 
Patient Reported Outcome Measures: Change from baseline in the PROMIS-29 (Patient-Reported Outcomes Measurement Information System) and PROMIS upper extremity tests. The PROMIS-29 is a free publicly available generic health related quality of life (HRQoL) measure consisting of indices of pain, pain interference, depression, anxiety, global function, and social interactions. The PROMIS upper extremity test utilizes item-response theory and Computer Adaptive Test to efficiently and precisely report patient symptoms and perceived function.

Secondary	
To determine the safety of treatment CBD.
 
Safety will be determined by evaluating:
 
 • The frequency and severity of adverse events from the beginning of treatment through the end of study participation. • Changes in skin appearance from baseline using standardized skin assessment tool (patient will be removed from study with a score ≥ 2) • Clinically significant change in CBC (baseline and weekly follow-up) • Clinically significant change in basic metabolic panel (i.e., BUN, creatinine, CO₂, Cl, K, Na, and glucose) (baseline and weekly follow-up) • Clinically significant change in hepatic function testing (i.e., serum transaminases [ALT/AST], total bilirubin, and alkaline phosphatase) (baseline and weekly follow-up) • Clinically significant change in vital sign assessments (i.e., heart rate and blood pressure) • Suicidal behavior and thoughts as a specific question using the Columbia-Suicide Severity Rating Scale (C-SSRS) at baseline and follow-up.

